9.4.2 Analysis of the Primary Efficacy Endpoint

The primary efficacy analysis is a stratified log-rank test, where stratification is according to baseline disease severity as defined by ordinal scale. Deaths will be considered as never recovering and censored at Day 29. In ACTT-3, the analyses conducted will depend on the results from ACTT-1 according to [Table 4](#).

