3.3.2. Recovery and Time to Recovery

The primary efficacy and one of the key secondary outcome measures is the time to recovery assessed through Day 29 + 6 days. Recovery will be defined as having a value of 1, 2, or 3 on the clinical status 8-point ordinal scale. The time to recovery will be defined as the elapsed time (in days) from randomization to the earliest day at which a subject reaches recovery. Note that since clinical status assessments are recorded as defined in Section 4.3, the day that is being assessed (not necessarily the day the response is collected) will be used to determine the timing of events. For example, a subject with a score of 5 recorded on Days 1-3 and a score of 3 recorded on

Day 4 will have a time to recovery equal to 3 days. It is also possible that a subject has a clinical status score > 3 reported for a particular day but was subsequently discharged on the same day. Such cases and other special cases will be reviewed by the Endpoint Review Committee or the NIAID Medical Officer, or her designee(s), to make the determination of whether the subject should be considered recovered in analyses. Subject data to be reviewed as part of this determination will include the reported clinical status scores while hospitalized, where the subject was discharged to (e.g. private residence, rehabilitation facility, long-term care/nursing home, comfort and care), and any information regarding readmittance. Subjects discharged to hospice or other end-of-life care will not be considered recovered. Additional information may be solicited to assess recovery.

Any subjects that are lost to follow-up or terminated early prior to an observed recovery will be censored at the day of their last observed assessment. Subjects who complete follow-up but do not experience recovery will be censored at the day of their Day 29 visit. All deaths that occur on or before Day 29 (and prior to any observed recovery) will be considered censored at 28 days. Note that we do not expect many subjects to worsen after discharge. However, we will evaluate whether any discharged subjects subsequently experience a worse clinical status and sensitivity analyses will be conducted accordingly. For these analyses, subjects who recover but are later readmitted for COVID-19 will not be considered a recovery but will instead be censored at 28 days.

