3.3.4. Time to Clinical Status Improvement

Additional analyses will evaluate the time to improvement of at least one point on the clinical status 8-point ordinal scale. That is, improvement will be defined as a decrease of at least one point on the 8-point scale compared to the baseline value (e.g. from 5 to 4; from 5 to 3) and the time to improvement will be defined as the elapsed time (in days) from randomization to the earliest day of observed improvement. Note that since clinical status assessments are recorded as defined in Section 4.3, the day that is being assessed (not necessarily the day the response is collected) will be used to determine the timing of events.

For analyses of this outcome, imputation of the clinical score may be performed following the rules described in Section 6.5.

Any subjects that are lost to follow-up or terminated early prior to an observed improvement will be censored at the day of their last observed assessment. Subjects who complete follow-up but do not experience improvement will be censored at the day of their Day 29 visit. All deaths that occur on or before Day 29 (and prior to any observed improvement) will be considered censored at 28 days.

An alternative definition of improvement will also be used where improvement will be defined as a decrease of at least two points on the 8-point scale compared to the baseline value (e.g. from 5 to 3; from 5 to 2). The timing and censoring definitions will follow similarly to the above.

3.3.5. Time to Discharge or NEWS of ≤ 2

The time to discharge or NEWS of ≤ 2 will be defined as the elapsed time (in days) from baseline to the earliest day at which either of the following occur:

- Discharge from hospital, unless discharged to hospital or end-of-life care.
- Reported NEWS of ≤ 2 which is maintained for 24 hours

For the latter bullet, to meet this criterion, scores of ≤ 2 must be reported on consecutive study visits. The timing of the event will be set to the day of the second assessment. Subjects who enroll with a baseline NEWS of ≤ 2 must be discharged from the hospital to meet this endpoint.

All deaths or discharge to hospice or other end-of-life care that occur before discharge or before an observed NEWS of ≤ 2 will be considered censored at 28 days.

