6.5. Missing Data

All attempts will be made to collect all data per protocol. Any data point that appears to be erroneous or inexplicable based on clinical judgment will be investigated as a possible outlier. If data points are identified as outliers, sensitivity analyses may be performed to examine the impact of including or excluding the outliers. Any substantive differences in these analyses will be reported.

For time to event outcomes, subjects who are lost to follow-up or terminate the study prior to Day 29 and prior to observing/experiencing the event will be censored at the time of their last observed assessment. Subjects who die prior to observing/experiencing the event will be censored at Day 29.

For the analysis of the key secondary outcome, subjects who are discharged but are subsequently re-admitted prior to Day 15 without a reported clinical score, their clinical score will be imputed at 7, which is the highest value for a hospitalized subject.

For the analyses of the secondary outcomes that involve clinical score (i.e. the key secondary outcome and time to improvement), if a subject is discharged from the hospital (but not to hospice or other end-of-life care) without a previously or concurrently reported clinical score of 1 or 2, then their clinical score at the time of discharge will be imputed as 2, which is the highest value for a non-hospitalized subject. If a subject terminates early from the study while they are

hospitalized or completes the study while still hospitalized, the last observed clinical score assessment will be used as their final assessment.

For the modified version of the ordinal score described in Section 4.3, if a subject is discharged from the hospital without a previously or concurrently reported clinical score of 2 or 3, then their clinical score at the time of discharge will be imputed as 3, which is the highest value for a non-hospitalized subject.

For the analyses of the secondary outcomes described in Section 3.3, the following imputation rules will be used for subjects who are lost to follow-up, terminate early from the study, or do not have further outcome data available after discharge for any reason:

- NEWS Total score (any missing study day)
 - If the subject dies or is discharged to hospice or other end-of-life care prior to the missing study day, the worst NEWS score (20) will be imputed

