8. EFFICACY EVALUATION

8.1. Primary Efficacy Analysis

8.1.1. Primary Analysis of Time to Recovery

The primary analysis uses the stratified log rank test to compare treatment to control through Day 29 with respect to time to recovery, as defined in Section 3.3. Stratification is based on ordinal scale at baseline (4, 5, or 6). As noted in Section 3.3, all deaths within 29 days will be considered censored at Day 29 with respect to time to recovery. Conceptually, a death corresponds to an infinite time to recovery, but censoring at any time greater than or equal to Day 29 gives the same answer as censoring at Day 29; both correspond to giving deaths the worst rank.

As noted in Section 6.6.3, to maintain an overall two-sided type-I error rate of 0.05, the Lan-DeMets spending function analog of the O'Brien-Fleming boundary will be used to derive the cumulative error spending and boundaries for the interim analysis.

For the final analysis, the log rank test will be performed using the pseudocode provided in Section 6.1. The following pseudocode can be used to compute the bounds for the final analyses and compare to the calculated log-rank statistic. The Boundaries dataset will contain the updated boundaries calculated from the interim analyses using the actual information levels observed at the interim analysis.

```

dataParms_LogR;
  set logrankp(rename=(Statistic=Estimate));
  if Variable='TreatmentVariable';
  _Scale_='Score';
  _Stage_=AnalysisNumber;
  keep Variable _Scale_ _Stage_ StdErr Estimate;
run;

proc seqtest Boundary=Boundaries
 Parms (Testvar=TreatmentVariable)=Parms_LogR
  infoadj=prop
  boundaryscale=score
  ;
  ods output Test=FinalResults ParameterEstimates = LogHRest;
run;

```

If the trial is stopped at the interim analysis, then to derive the p-value, hazard ratio estimate, and confidence interval for the early and final analysis sets, stage-wise ordering of the sample space will be used [5]. The resulting p-value, median unbiased estimate, and confidence interval will be presented in the final report. If the trial is not stopped early, then the fixed sample estimates of the statistics using an alpha level of 5% will be computed and reported for the final analysis. The SAS pseudocode above provides estimates for the log hazard ratio and so the estimates will be exponentiated and reported.

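### Time to recovery censors unrecovered subjects who leave after hospice discharge or for terminal illness at their last assessment, although deaths are held to 28 days

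*SAP*

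**What the plan says.** SAP 3.3.2 states that subjects "lost to follow-up or terminated early prior to an observed recovery will be censored at the day of their last observed assessment". SAP 6.5 repeats this for time-to-event outcomes in general: such subjects "will be censored at the time of their last observed assessment". Neither section makes an exception for the reason for leaving.

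Deaths are handled differently. SAP 3.3.2: "All deaths that occur on or before Day 29 (and prior to any observed recovery) will be considered censored at 28 days". SAP 8.1.1 explains that censoring deaths at Day 29 or at any later time gives the same answer, since "both correspond to giving deaths the worst rank". Protocol Appendix C 9.4.2 agrees: "Deaths will be considered as never recovering and censored at Day 29". (Day 29 is 28 elapsed days from Day 1, so the two labels match.)

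On hospice, SAP 3.3.2 says only: "Subjects discharged to hospice or other end-of-life care will not be considered recovered". It gives no censoring day. A hospice subject who then leaves the study therefore falls under the general last-assessment rule.

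The NEWS endpoints group hospice with death. SAP 3.3.5 covers "All deaths or discharge to hospice or other end-of-life care that occur before discharge" or before the NEWS target, and holds both to 28 days. SAP 6.5 imputes the worst NEWS total, 20, for both.

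**The concern.** Censoring at the last assessment assumes that the subject would have gone on to recover at the same rate as those still at risk. That is implausible for someone who has gone to hospice or has left for comfort care. Such a subject is close to the position of a death, which the SAP deliberately keeps in the risk set to the end. Protocol Appendix C 5.6.2 describes terminal-illness requests as a common lost-to-follow-up scenario in ACTT-1, so the route is real, although no rate is given.

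If one arm has more of these exits, removing them early from the risk set understates that arm's excess of failures in the primary hazard ratio. The primary p-value also decides whether p-values are reported for the key secondary endpoints and for mortality (SAP 6.8).

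**Working it through.** **The plan's own figures.** SAP 5: E = 4(1.96 + z)²/(ln θ)². With θ = 1.25 and z = 1.036 (85% power), E = 4 × 2.996²/0.2231² = 721, against the stated 723, a negligible difference. 831/0.90 = 923, as stated. With 831 recoveries and 1:1 allocation, SE(log HR) = 2/√831 = 0.0694.

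**How SAP 3.3.2 sorts unrecovered subjects.**

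| Course | Censored at |
|---|---|
| Death recorded by Day 29 | 28 days |
| Completes follow-up, including after hospice discharge | Day 29 visit |
| Leaves early for any reason, including terminal illness or after hospice discharge, no death recorded | last assessment |

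Only the last row is in question, and only its end-of-life part.

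**Size, first simulation.** Every rate here is an assumption. In each arm 3% die and 4% stay alive and unrecovered. About 461 subjects per arm; recoverers' median 6 days (lognormal, sigma 0.7); exits' median day 8 (sigma 0.5). Whole-day data, Cox model with Efron ties, runs of 1,000,000 subjects, Monte Carlo SE about 0.001 in the no-effect runs. Shift = ln(HR under SAP rule / HR with exits held to 28 days) / 0.0694.

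| Exits, interferon v placebo | HR, SAP rule | HR, held to 28 days | Shift |
|---|---|---|---|
| No effect, 2% v 2% | 1.001 | 1.001 | none |
| No effect, 4% v 4% | 1.000 | 1.000 | none |
| Effect, 2% v 2% | 1.246 | 1.235 | 0.011 in HR |
| Effect, 4% v 4% | 1.239 | 1.219 | 0.020 in HR |
| No effect, 2% v 1% (about 9 v 5) | 0.986 | 0.972 | 0.20 SE |
| No effect, 4% v 2% (18 v 9) | 0.973 | 0.947 | 0.38 SE |
| No effect, 6% v 2% (28 v 9) | 0.945 | 0.899 | 0.71 SE |

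The shifts come from unrounded ratios; the rounded ratios give 0.21, 0.39 and 0.72. The last row is extreme, since it assumes twice as many exits as the 3% recorded deaths. At 4% v 2% the shift is 0.57 SE with exits around day 4 and 0.19 SE around day 14. It is 0.31 to 0.37 SE when the death rate or recovery speed is varied.

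**Size, second simulation.** 1,500 trials of 923 subjects; exponential recovery with 90% of controls recovered by day 28; exits on days 3 to 10.

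- No effect, 3% v 1%: 0.985 to 0.951, ln(0.985/0.951)/0.0694 = 0.51 SE.
- No effect, 5% v 2%: 0.983 to 0.933, 0.75 SE.
- True ratio 1.25 among the other subjects, 5% v 5%: 1.236 to 1.202, about 0.03.
- True ratio 1.25 among the other subjects, 5% v 2%: 1.210 to 1.121.
- No effect, equal exits: both rules reject in about 2.5% to 3.5% of trials per side.

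**Power with equal exits.** Power = Φ(ln HR/0.0694 − 1.96), using the first simulation's ratios. At 2% v 2%: ln 1.246/0.0694 − 1.96 = 1.21, giving 88.7%; ln 1.235/0.0694 − 1.96 = 1.08, giving 86.0%. At 4% v 4%: 87.1% falls to 81.4%.

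**The case against.** The case for leaving the plan alone has real substance.

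- **The subset is small.** The scenario in Protocol Appendix C 5.6.2 is a request to stop study product and blood draws. The stated response is to keep the subject in the study for the Day 29 score by chart review or phone. Sections 7.1.1 and 7.2 say the same, 7.3 counts a subject as lost only if all of Days 15, 22 and 29 are missed, and categories 6 and 7 are no longer enrolled. This stands.
- **An imbalance would be visible.** Table 4 gives status at termination by arm, Figure 2 shows terminations by study day and hospitalization status, and Table 17 groups deaths with non-recoveries. This stands, but none of them yields a hazard ratio.
- **The Day 15 key secondary keeps in-hospital exits at their last score** (SAP 6.5), so they remain unrecovered there. This stands for that endpoint only.
- **The precedent is limited.** SAP 3.3.5 covers hospice discharge, not early termination for terminal illness, and SAP 3.3.4 uses the same last-assessment rule as 3.3.2. This stands, and it is why the primary-analysis change below stops at hospice.
- **The imbalance is assumed.** A split of 18 v 9 among 27 exits has an exact two-sided p of about 0.12, so chance alone could produce it. This stands.

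What the objection does not supply is a specified analysis that re-censors these subjects. Fine-Gray codes deaths only, the review committees (SAP 3.3.2, Protocol Appendix C 9.3) are given no censoring day to apply, and other censoring techniques are optional (SAP 8.1.2).

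**Conclusion.** The point holds as a cheap improvement. A stated rule produces informative censoring for a small, identifiable subset, and it departs from the SAP's own handling of hospice discharge in the NEWS endpoints. The shift is about 0.2 to 0.4 SE at 2% v 1% to 4% v 2% exits in the base case, and larger if exits are earlier or more unequal. With equal exits it is 0.02 or less in the hazard ratio up to 4% per arm, and about 0.03 at 5% v 5%. All of this rests on assumed exit rates, timing and imbalance.

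A reader might infer more than the documents support:

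- **That the primary test is biased or its type I error inflated.** With equal exits and no effect the hazard ratio does not move, and no document shows unequal exits.
- **That terminally ill subjects are dropped as a group.** Those who stay in follow-up, and those whose death is recorded by Day 29, are already held to the end.
- **That every terminal-illness termination belongs at 28 days in the primary analysis.** That is debatable, and SAP 3.3.5 is no precedent for it, so it belongs in a sensitivity analysis.
- **That the death rule is at fault.** It is sound.

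**What to change.** Before unblinding:

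1. In SAP 3.3.2, for time to recovery only, state that unrecovered subjects discharged to hospice or other end-of-life care are censored at 28 days, as deaths are and as 3.3.5 already does. Cross-refer from 6.5, worded so that time to improvement (3.3.4) and time to death (3.3.10) do not change. Discharge destination is already among the data to be reviewed under 3.3.2.
2. In SAP 8.1.2, prespecify one sensitivity analysis that censors at 28 days everyone who terminates early while hospitalized and unrecovered, including terminal-illness and comfort-care exits. It uses the status data planned for Table 4 and needs no separate code for terminal illness. Listing 2 records a reason for termination, but nothing shows that such a code exists.

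Leave the primary rule for other early terminations, the death rule and the event target unchanged.

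The cost is wording in SAP 3.3.2, 6.5 and 8.1.2 and one extra analysis. If treatment works and hospice exits are balanced, the estimated ratio and power fall slightly: from about 89% to 86% if 2% of each arm were moved to 28 days, which is an assumed rate. Fixing the rule now avoids choosing a censoring technique after the arms are known.

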3.3.3. Clinical Status at Specific Timepoints

The key secondary analyses include evaluation of the clinical status score at Day 15. For this outcome, Study Visit Day 15 is the timepoint of interest, not necessarily the actual study day. The score collected at the study visit corresponding to Day 15 will be used for this outcome. For analyses of this outcome, imputation of the clinical score may be performed following the rules described in Section 6.5.

Additional analyses are clinical status at Days 3, 5, 8, 11, 15, 22, and 29. As the with above, the scores that will be used are those collected at the study visits corresponding to those days.

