8.1.2 Efficacy Assessments

8.1.2.1 Measures of clinical support, limitations and infection control

The subject's clinical status, which is largely measured by the ordinal scale and NEWS, will be captured on each study day while hospitalized through Day 29 (+ 6-day window) or day after death whichever comes first. The ordinal scale will also be captured on the day after discharge from the hospital. This will be done so that discharge and death are accurately recorded and captured in the eClinical system. For subjects who received oxygen by nasal cannula or CPAP ventilatory support at night at home prior to having COVID-19, sites should assign a recovery ordinal scale score of 1 or 2 when discharged to home after recovery. The assignment of category 1 versus category 2 will depend on whether they have new or increased physical limitations post-COVID-19 and/or if they have new or increased home oxygen requirement compared with the pre-COVID-19 time period.

It is important to capture all deaths that occur during the study as this is one of the outcomes of the study. Death is a category on the ordinal scale. If a subject dies during the study, an ordinal scale assessment should be completed for the day after death because the ordinal scale captures the worst clinical assessment for the previous day. If a subject dies within the window of the final study visit (i.e., Day 29 + 6-day window), complete an ordinal scale assessment on the day after death.

If a subject is discharged prior to Day 15, clinical status is collected on Day 15 and 29 if the subject returns for an in-person clinic visit or by phone, home visit or remote telehealth procedure as per institutional standards if an in-person visit at the clinical trial site is not possible. Clinical status will also be captured on Day 22 during a phone call or remote telehealth visit. Unlike the NEWS, the ordinal scale can also be evaluated over the phone or by a remote telehealth procedure if the discharged subject is unable to return to the clinical trial site for visits on Day 15 and 29 as well as on Day 22.

Except for Day 1, when the ordinal scale and the NEWS is captured at the time of randomization, a site should try to complete the ordinal scale and the NEWS at approximately the same time each day. Ideally, complete the ordinal scale concurrently with NEWS just prior to study product administration, as time permits. The following measures are recorded for the ordinal scale:

- Hospitalization.

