8.1.2.2 Ordinal Scale

The ordinal scale is the primary measure of clinical outcome. The scale used in this study is as follows (from worst to best), and categories 1, 2 and 3 represent recovery for a subject:

Category 8: Death;

Category 7: Hospitalized, on invasive mechanical ventilation or ECMO;

Category 6: Hospitalized, on non-invasive ventilation or high flow oxygen devices;

Category 5: Hospitalized, requiring supplemental oxygen;

Category 4: Hospitalized, not requiring supplemental oxygen – requiring ongoing medical care (COVID-19 related or otherwise);

Category 3: Hospitalized, not requiring supplemental oxygen – no longer requires ongoing medical care; This would include those kept in hospital for quarantine/infection control, awaiting bed in rehabilitation facility or homecare, etc.

Category 2: Not hospitalized, but new or increased limitation on activities and/or requiring new or increased home oxygen;

Category 1: Not hospitalized, no limitations on activities

To determine a subject's clinical status using the ordinal scale: On Day 1, report their clinical status at randomization. As there should be <24 hours between randomization and infusion, the ordinal scale at done at randomization suffices as the Day 1 ordinal scale. After Day 1, collect the ordinal scale daily while hospitalized from Day 2 through Day 29 by providing the worst clinical assessment for the previous day (i.e., midnight to midnight; 00:00 – 23:59 (24-hr clock)).

For those who are discharged prior to Day 15, collect ordinal scale on follow-up Days 15, 22 and 29 by providing the worst clinical assessment for the previous day (i.e., midnight to midnight; 00:00 – 23:59 (24-hr clock)). For example, on study Day 3 when completing the form, the worse clinical outcome measure of Day 2 is captured with the worst being death followed by ECMO, mechanical ventilation, etc. The Day 2 measurement is assessed as occurring anytime in that 24-hour period (00:00 to 23:59).

It is important to capture all deaths that occur during the study as this is one of the outcomes of the study. Death is a category on the ordinal scale. If a subject dies during the study, the site will need to complete an ordinal scale assessment for the day after death. If a subject dies within the window of the final study visit (i.e., Day 29 + 6-day window), complete an ordinal scale assessment on the day after death. For more information about the data collected for the ordinal scale, see the MOP.

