3.2. Endpoints

Primary Endpoint

Time to recovery, where recovery is defined as clinical status in states 1, 2, or 3 of the 8-point ordinal scale, through Day 29 (+6).

- Clinical status of a subject (8-point ordinal scale) is defined below:
 8. Death;
 7. Hospitalized, on invasive mechanical ventilation or ECMO;
 6. Hospitalized, on non-invasive ventilation or high flow oxygen devices;
 5. Hospitalized, requiring supplemental oxygen;
 4. Hospitalized, not requiring supplemental oxygen - requiring ongoing medical care (COVID-19 related or otherwise);
 3. Hospitalized, not requiring supplemental oxygen - no longer requiring ongoing medical care;
 2. Not hospitalized, but new or increased limitation on activities and/or requiring new or increased home oxygen;
 1. Not hospitalized, no limitations on activities

Secondary Endpoints

The key secondary endpoints are:

- Clinical status (8-point ordinal scale) on Day 15.
- Time to recovery, where recovery is defined as clinical status in states 1, 2, or 3 of the 8-point ordinal scale, through Day 29 (+6).

The other secondary endpoints are:

- Ordinal outcome assessed while hospitalized (Days 3, 5, 8, 11) and on Days 15, 22, and 29.
- NEWS assessed daily while hospitalized (Days 3, 5, 8, 11) and on Days 15 and 29.
- Days of supplemental oxygen (if applicable).
- Days of non-invasive ventilation/high-flow oxygen (if applicable).
- Days of invasive mechanical ventilation/ECMO (if applicable).
- Days of hospitalization.
- Date and cause of death (if applicable).
- D-dimer and CRP on Day 1, while hospitalized (Days 3, 5, 8, 11), and on Days 15 and 29.
- SAEs.
- Grade 3 and 4 adverse events

- WBC with differentials, hemoglobin, platelets, creatinine, total bilirubin, ALT, AST, INR, d-dimer, and CRP on Day 1; Days 3, 5, 8, and 11 (while hospitalized); and Days 15 and 29 (if attends in-person visit or still hospitalized).

Exploratory Endpoints (not described in this SAP)

- Qualitative and quantitative polymerase chain reaction PCR for SARS-CoV-2 in OP swab on Day 1; Days 3, 5, 8, and 11 (while hospitalized); and Days 15 and 29 (if attends in-person visit or still hospitalized).
- Deep sequencing of the SARS-CoV-2 virus for those subjects with sustained vial shedding
- Qualitative and quantitative PCR for SARS-CoV-2 in blood on Day 1; Days 3, 5, 8, and 11 (while hospitalized).

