6. GENERAL STATISTICAL CONSIDERATIONS

6.1. General Principles

This is a double-blind, placebo controlled randomized trial with a two-sided type I error rate of 0.05. Secondary hypotheses have been ordered according to relative importance. These will be described according to the appropriate summary statistics, e.g.:

- Percentages/proportions/odds ratios for categorical data. For tabular summaries of percentages/proportions, the denominator (e.g. number of subjects with non-missing data) will be displayed.
- Means, median, and range for continuous data, median for time-to-event data.

Confidence intervals will be generated; for the primary analysis, the confidence level will take into account the group-sequential design of the trial (see Section 6.6 and Section 8.1) whereas 95% confidence intervals will be generated for secondary and exploratory outcomes. For hazard ratio and odds ratio estimates, Wald confidence intervals will be used. For other efficacy outcomes (e.g. proportions), Wilson or Score confidence intervals will be used. For safety outcomes, exact (e.g., Clopper-Pearson) confidence intervals will be used.

When calculating treatment effects (e.g., differences, hazard ratios, odds ratios) and when using treatment arm as a covariate in regression modeling, the placebo + remdesivir arm will be used as the reference group. For regression modeling that uses strata variables defined in Section 6.4, the first stratum listed for each variable in that section will be used as the reference group.

For the final time-to-event analyses, the following SAS pseudocode will be used to perform stratified analyses to generate stratum-specific median time to event estimates and confidence intervals, stratum-specific Kaplan-Meier curves, and to perform the log-rank test. For any unstratified analyses, code can be used after the removal of the `strata ... ;` line.

```
proc lifetest data=dataset plots=(s);
  time TimeVariable * CensorVariable(1);
  strata StrataVariable;
  test TreatmentVariable;
run;
```

Note that the interim efficacy analyses will be performed using R. For all interim and final analyses, the software used will calculate the log rank statistic using the formula in Section 8.1.1.

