	Hospitalized, not requiring supplemental oxygen - requiring ongoing medical care (COVID-19 related or otherwise) (4)	x	x	x.x, x.x	x	x	x.x, x.x	x.x	x.x, x.x
	Hospitalized, not requiring supplemental oxygen - no longer requires ongoing medical care (3)	x	x	x.x, x.x	x	x	x.x, x.x	x.x	x.x, x.x
	Not hospitalized, but new or increased limitation on activities and/or requiring new or increased home oxygen (2)	x	x	x.x, x.x	x	x	x.x, x.x	x.x	x.x, x.x
	Not hospitalized, no limitations on activities (1)	x	x	x.x, x.x	x	x	x.x, x.x	x.x	x.x, x.x
[Repeat for Study Visit Days 3, 5, 8, 11, 15, 22, and 29]									

N = Number of Subject in the mITT Population.

n = Number of subjects who reported the respective score

95% CI calculated using Wilson CIs

Tables with similar format:

Table 24: Clinical Status Scores by Treatment Group and Study Visit – mITT Population, Baseline Ordinal Score of 6

Table 25: Clinical Status Scores by Treatment Group and Study Visit – mITT Population, Baseline Modified Oxygen Use Ordinal Score of 4 or 5

Table 26: Clinical Status Scores by Treatment Group and Study Visit – mITT Population, Baseline Modified Oxygen Use Ordinal Score of 6

Programming notes for Table 25 and Table 26:

The tables will include the footnote: This analysis used a modified version of the ordinal scale where the definitions of categories 5 and 6 are, respectively, “Hospitalized, requiring supplemental oxygen or high flow oxygen devices at oxygen flow rate less than or equal to 15L/min” and “Hospitalized, on non-invasive ventilation or high flow oxygen devices at oxygen flow rate greater than 15L/min”.

Table 27: Summary of Clinical Status Score by Treatment Group and Study Visit – mITT Population, Baseline Ordinal Score of 4 or 5

Study Visit	Statistic	Interferon beta-1a + RDV (N=X)	Placebo + RDV (N=X)	Difference
Baseline	Number of reported clinical scores	x	x	--
	Mean (95% CI)	x.x (x.x, x.x)	x.x (x.x, x.x)	x.x (x.x, x.x)
	Median	x.x	x.x	x.x (x.x, x.x)
	Range (Min, Max)	x, x	x, x	--
Day 3	Number of reported clinical scores	x	x	--
	Mean (95% CI)	x.x (x.x, x.x)	x.x (x.x, x.x)	x.x (x.x, x.x)
	Median	x.x	x.x	x.x (x.x, x.x)
	Range (Min, Max)	x, x	x, x	--
Change from Baseline Mean (95% CI)		x.x (x.x, x.x)	x.x (x.x, x.x)	--
Continue for Days 5, 8, 11, 15, 22, 29				
N = Number of subjects in the mITT Population.				
Missing values were imputed using Last Observation Carried Forward. Clinical scores of 8 were carried forward from the date of death for subjects who died.				

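### Clinical status at Days 3, 5, 8 and 11 (SAP Tables 23-26) has no score rule for most patients already discharged, while deaths are carried forward

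*SAP*

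**What the plan says.** **Collection.** Appendix C of the protocol, section 8.1.2.2, has sites "collect the ordinal scale daily while hospitalized from Day 2 through Day 29". It continues: "For those who are discharged prior to Day 15, collect ordinal scale on follow-up Days 15, 22 and 29". Section 8.1.2.1 adds one more score: "The ordinal scale will also be captured on the day after discharge from the hospital". SAP 3.2 describes the endpoint in the same way: "Ordinal outcome assessed while hospitalized (Days 3, 5, 8, 11) and on Days 15, 22, and 29".

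**Score used.** SAP 3.3.3 takes the score from the matching visit: "the scores that will be used are those collected at the study visits corresponding to those days". It mentions imputation under SAP 6.5 for the Day 15 outcome only.

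**Imputation.** SAP 6.5 gives a discharged patient a score of 2, unless discharge was to hospice or other end-of-life care. It limits this rule to the key secondary outcome and time to improvement. Its further rules cover NEWS, days of respiratory support, days in hospital, and d-dimer and CRP. None covers clinical status by visit.

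**Tables.** The Table 23 shell, which Tables 24-26 follow, shows all eight categories at each visit with risk differences and 95% CIs. Its worst row counts deaths at or before the visit. The footnote says "n = Number of subjects who reported the respective score" and gives the header N as the mITT population. It does not name the percentage denominator. SAP 6.1 says of percentages in general that "the denominator (e.g. number of subjects with non-missing data) will be displayed". Table 27, and Table 28 in the same format, do state a rule: "Missing values were imputed using Last Observation Carried Forward. Clinical scores of 8 were carried forward from the date of death for subjects who died".

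**The concern.** Together these rules treat the two ways of leaving the ward differently. A patient who dies on Day 4 is counted in category 8 at Days 5, 8 and 11. A patient who goes home on Day 4 is scored on Day 5 and then has nothing to count at Day 8 or Day 11. The rows where a benefit should show, categories 1 and 2, are the ones left nearly empty.

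Clinical status on these days is a stated secondary objective, and the visits span the dosing period (injections on Days 1, 3, 5 and 7). The plan solves the same problem elsewhere: NEWS gets a score of 2 after discharge for any missing study day, and Tables 27-28 carry the last observation forward. That suggests an oversight in Tables 23-26, not a deliberate choice. With two denominators open, the choice could also be made after unblinding.

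**Working it through.** The documents give no figure for this point, so its size can only be illustrated.

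**Inputs from SAP Section 5.** Recovery rate ratio 1.25 and about 90% recovered within 28 days. Both agree with the plan's own arithmetic:
- 4(1.96 + 1.036)² / (ln 1.25)² = 721.3, or 722 events, against the stated 723.
- 831 / 0.90 = 923.3, against the stated 923.

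**Assumptions, not in the documents.** Recovery is taken as discharge, with exponential timing. The 90% applies to the control arm. In both arms 5% of all randomized patients are ventilated. Deaths and readmissions are ignored.

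**Formulas.** Daily rate λ = ln(10)/28 = 0.0822 in control and 1.25λ = 0.1028 with interferon. At visit Day d, let t = d − 1.
- Truly out of hospital: 1 − exp(−λt).
- No score, because discharge was more than a day earlier: u = 1 − exp(−λ(t − 1)).
- Out of hospital and scored: the first line minus u.
- Ventilated among scored patients: 0.05/(1 − u).

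Results in percent as control / interferon; differences in points, interferon minus control:

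| Day | Truly out | True diff. | No score | Diff. seen, mITT N | Diff. seen, scored N | Ventilated among scored | Spurious diff. |
|---|---|---|---|---|---|---|---|
| 3 | 15.2 / 18.6 | +3.4 | 7.9 / 9.8 | +1.5 | +1.9 | 5.4 / 5.5 | +0.1 |
| 5 | 28.0 / 33.7 | +5.7 | 21.9 / 26.5 | +1.0 | +1.9 | 6.4 / 6.8 | +0.4 |
| 8 | 43.8 / 51.3 | +7.5 | 38.9 / 46.0 | +0.5 | +1.9 | 8.2 / 9.3 | +1.1 |
| 11 | 56.1 / 64.2 | +8.2 | 52.3 / 60.4 | +0.1 | +1.9 | 10.5 / 12.6 | +2.1 |

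For example, at Day 11 in control, u = 1 − exp(−0.0822 × 9) = 0.523 and 0.05/0.477 = 10.5%. With interferon, 0.05/0.396 = 12.6%.

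With mITT N the ventilated share is 5% in each arm at every visit, so that spurious difference is 0. The loss is then confined to categories 1 and 2, and each column falls short of 100% by the unscored share.

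**Range.** Use instead a control median of 10 days, the ACTT-1 remdesivir figure in SAP Section 2 (λ = ln 2/10). At Day 11, 46.4% / 54.1% have no score. The true out-of-hospital difference of +8.0 points appears as +0.2 (mITT N) or +1.6 (scored N). The spurious ventilation difference with scored N is 1.6 points (9.3% against 10.9%).

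**The case against.** The strongest reply is that Table 23 means to place every mITT patient in a category. Its header N is the mITT population, it prints the two not-hospitalized rows at every visit, and its death row is cumulative. SAP 6.1 offers non-missing patients only as an example and requires the denominator to be shown. On that view one footnote is missing and nothing is biased.

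Part of this stands. The layout does suggest that discharged patients were meant to be counted, and with mITT N the in-hospital rows are not distorted. But no rule supplies the discharged patients' scores. SAP 3.3.3 opens its second paragraph by likening these days to Day 15, but what it then repeats is the use of the visit's score. Section 6.5 names the two outcomes it covers, and this is not one of them. Programmed as written, categories 1 and 2 stay nearly empty even with mITT N.

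It is also fair that the tables are descriptive, with no p-value column. Tables 23 and 27 serve separately listed objectives (status by day, and mean change), so their different handling is untidy but not a contradiction.

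**Conclusion.** The point holds. As written, Tables 23-26 omit most discharged patients from the out-of-hospital categories at Days 3-11 while keeping all deaths. In the illustration about half or more of each arm has no score at Day 11. A true out-of-hospital difference of about 8 points appears as 0.1 to 1.9 points, depending on denominator and discharge rate. These sizes rest on exponential discharge and an assumed 5% ventilated. Recovery includes patients still in hospital in category 3, so treating it as discharge overstates how many have left.

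Three stronger readings are not supported:
- **That the tables will show false harm from interferon.** This needs the non-missing denominator, which Table 23 does not state, and faster discharge on interferon.
- **That the distortion is much larger.** Ignoring the day-after-discharge score raises the Day 11 figure to +2.6 points (0.05/0.439 = 11.4% against 0.05/0.358 = 14.0%), but the protocol collects that score. A 5-day control median would give more, but it implies 1 − 2^(−28/5) = 98% out by 28 days, at odds with the plan's 90%.
- **That the main conclusions are at risk.** Time to recovery, the Day 15 key secondary outcome, the Day 22 and 29 results and Tables 27-28 are not affected in this way.

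It should be corrected before unblinding, as a fault in descriptive secondary tables.

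**What to change.** In SAP 3.3.3 and the footnotes to Tables 23-26, state that:
- the day-after-discharge score is carried forward to the next scheduled assessment; if it is absent, the SAP 6.5 discharge score is used, keeping that section's exclusion of discharge to hospice or end-of-life care;
- patients readmitted are scored from their daily scores, which Appendix C section 7.4 already requires;
- death is carried forward as 8;
- the percentage denominator is all mITT patients in the baseline-score group.

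The cost is a few lines of SAP text and one programming rule, with no new data. The small downside is that a carried-forward home status can miss a readmission that was not reported.
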